7.2. Summary of Nonclinical Studies

A brief summary of key findings from pharmacology and toxicology studies is provided below. A comprehensive review of ACE-536, as well as details regarding the information summarized below, is provided in the Investigator's Brochure (IB). The most recent version of the ACE-536 IB should be reviewed prior to initiating the study.

7.2.1. Pharmacology Studies

In vitro and in vivo nonclinical pharmacology studies have been conducted with ACE-536 or its murine ortholog, RAP-536. The RAP-536 molecule has the same ECD as ACE-536, but contains a murine IgG Fc domain in place of the human IgG Fc. The RAP-536 ortholog is substantially less immunogenic in rodent species and therefore permitted the conduct of longer term pharmacology studies in rodents without the confounding influence of immune reactivity.

ACE-536 has been shown to have significant effects on erythropoiesis. Evidence suggests that it binds ligands that normally act to modulate the differentiation of late-stage erythroid precursors (normoblasts). Inhibition of these ligands leads to a rapid and robust erythroid response and increased production of mature erythrocytes. Because ACE-536 affects late-stage erythrocyte precursor populations, its action is distinct from that of EPO. Unlike EPO, ACE-536 is not a growth-promoting cytokine.

Studies of ACE-536 in normal animals across several species (mice, rats, and cynomolgus monkeys) demonstrated an erythroid response that was rapid in onset, robust, and sustained. These effects were also demonstrated in a variety of animal models of anemia, including anemia associated with kidney failure, acute blood loss, and chemotherapy.

RAP-536 was shown to significantly improve hematologic parameters, including increased hemoglobin concentrations, and to correct ineffective erythropoiesis and anemia in mouse models of myelodysplastic syndromes (MDS) and β -thalassemia, both target indications for ACE-536. This is consistent with its proposed mechanism of action of driving the late stages of erythroid differentiation that is downstream and distinct from EPO.

The Hbb^{major/-} transgenic mouse was used to test RAP-536 in a model of β -thalassemia. This model represents human β -thalassemia intermedia, which is characterized by severe anemia, failure of erythroid differentiation, increased apoptosis of erythroid precursors, erythroid hyperplasia, splenomegaly and iron overload. Treatment with RAP-536 led to significant improvement in hematological parameters, including RBC and hemoglobin. Further effects of

treatment included decreased reticulocytes, red cell distribution width, EPO, bilirubin, RBC inclusion bodies, reactive oxygen species, serum ferritin, liver iron content (LIC), and spleen size, as well as increased hepcidin and bone mineral density, and improvements in RBC morphology.

Additional information regarding pharmacological effects of ACE-536 is summarized in the current version of the ACE-536 IB.

7.2.2. Toxicology Studies

Repeat-dose toxicology studies of 1 and 3 month treatment duration have been conducted with ACE-536 in Sprague-Dawley rats and cynomolgus monkeys to evaluate the toxicity of ACE-536. Recovery periods of up to 10 weeks were included as part of these studies. In addition, the main phase of a repeat-dose toxicology study of 6 months treatment duration in cynomolgus monkeys is complete. Findings from toxicology studies are described in more detail in the IB.

7.3. Summary of Clinical Experience

The safety, tolerability, pharmacokinetics (PK), and pharmacodynamics (PD) effects of ACE-536 was evaluated in healthy postmenopausal women in a phase 1, randomized, double-blind, placebo controlled, multiple ascending dose study (Study A536-02). The primary objective of the study is to evaluate the safety and tolerability of ACE-536 in this population. Secondary objectives of the study are to examine the PK parameters and PD effects of ACE-536.

A total of 32 subjects were enrolled. Eligible subjects were healthy, postmenopausal women, 45-75 years old. The anticipated PD effect was an increase in plasma hemoglobin level. Screening and baseline hemoglobin values had to be between 11.0 and 14.5 g/dL, inclusive, to mitigate the risk of substantial excursions above the normal range. Sequential cohorts of 8 subjects each were randomized to receive either ACE-536 (n=6) or placebo (n=2) administered as a SC injection on Day 1 and Day 15. Each subject was to be followed for 112 days (16 weeks) after receiving their last dose of ACE-536 or placebo. The following dose levels were evaluated: 0.0625, 0.125, and 0.25 mg/kg.

ACE-536 administered every 2 weeks by subcutaneous (SC) injection for one or two doses at dose levels of 0.0625, 0.125 or 0.25 mg/kg was generally safe and well-tolerated in healthy postmenopausal female subjects. No serious or severe adverse events (AE) were reported. The majority of AEs were considered mild in severity. AEs that were considered at least possibly drug-related across ACE-536 dose groups included injection site hemorrhage (3 subjects), injection site macule (2 subjects), and dry skin, macule, hyperesthesia, muscle spasms, myalgia, generalized pruritus, and papular rash (1 subject each). Injection site pain was reported in one placebo-treated subject.

PK results indicated mean AUC and C_{max} values increased in a dose-proportional manner with ACE-536 dose level; mean T_{max} ranged from 7.0 to 9.8 days, and mean $T_{1/2}$ ranged from 14.9 to 16.2 days after the first dose. These PK results support intermittent SC dosing of ACE-536 in future studies, e.g., every 3 weeks.

PD assessments for hematological markers showed increases in hemoglobin levels at the 0.125 mg/kg dose level and more consistently at the 0.25 mg/kg dose level. Small increases in

reticulocyte count and EPO levels were also observed at the two higher dose levels of ACE-536 investigated. A small decrease in serum follicle stimulating hormone (FSH) levels was observed at 0.25 mg/kg. These data support further studies of ACE-536 in conditions associated with ineffective erythropoiesis and anemia.

Two phase 2 studies with ACE-536 are ongoing. Study A536-03 is entitled, “A Phase 2, Open-Label, Ascending Dose Study of ACE-536 for the Treatment of Anemia in Patients with Low or Intermediate-1 Risk Myelodysplastic Syndromes (MDS)”. Study A536-04 is entitled “A Phase 2, Open-Label, Ascending Dose Study to Evaluate the Effects of ACE-536 in Patients with β -Thalassemia”. Preliminary results from these studies and additional information regarding the completed Phase 1 study can be found in the current version of the IB.

7.4. Potential Risks of Human Use

Increases in hematologic parameters (RBC, hemoglobin, hematocrit, reticulocytes) are expected pharmacologic effects of ACE-536 treatment. Increases in systolic and diastolic blood pressures may occur in concert with increases in hemoglobin values. Excessive or rapid increases in hemoglobin or blood pressure may occur and will be monitored. Dose modifications rules for individual patients and dose escalation/reduction rules will be utilized to minimize risks associated with increased RBC parameters.

AEs observed in the Phase 1 study in healthy volunteers and the ongoing phase 2 studies that were considered probably or possibly related to study drug included injection site reactions (hemorrhage, pruritus, rash), skin rash, hyperesthesia, muscle spasms, myalgia, pruritus, and hyperkalemia.

As with all biologics, there is the potential for anti-drug antibodies (ADA) that can be associated with increased drug clearance and hypersensitivity reactions. ADA formation against ACE-536 as well as human ActRIIB protein will be monitored in the initial clinical studies.

Repeat-dose toxicology studies of 1 and 3 month treatment duration have been conducted with ACE-536 in Sprague-Dawley rats and cynomolgus monkeys to evaluate the toxicity of ACE-536. In addition, the main phase of a repeat-dose toxicology study of 6 months treatment duration in cynomolgus monkeys is complete. Reproductive toxicity studies are currently ongoing with ACE-536 and therefore ACE-536 should not be administered to pregnant or nursing women. Male and female subjects of childbearing potential participating in studies of ACE-536 must be willing to abstain from sexual intercourse or use adequate contraception during treatment and for at least 12 weeks following the last dose of ACE-536. Please refer to the Investigator’s Brochure for additional information regarding findings from toxicology studies. It is unknown if humans will experience any of the effects of ACE-536 that were noted in the rat and monkey toxicology studies. Safety effects will be monitored closely through AE reporting, clinical laboratory tests, vital signs, and physical examinations. A comprehensive review of ACE-536, as well as details regarding the information summarized above, is provided in the IB. The ACE-536 IB should be reviewed prior to initiating the study.

8. TRIAL OBJECTIVES

8.1. Primary Objectives

- To evaluate the long-term safety and tolerability of ACE-536 in patients with β -thalassemia who were previously enrolled in study A536-04.

8.2. Secondary Objectives

- To evaluate erythroid response defined as the proportion of patients with:
 - Mean hemoglobin increase ≥ 1.5 g/dL over a continuous 12-week interval compared to baseline in non-transfusion dependent (NTD) patients, not influenced by RBC transfusion, OR
 - Reduction in RBC transfusion burden by $\geq 50\%$ over a continuous 12-week interval compared to the 12 weeks prior to the start of treatment in transfusion dependent (TD) patients.
- To evaluate erythroid response defined as proportion of patients with:
 - Mean hemoglobin increase ≥ 1.5 g/dL over a continuous 8-week interval compared to baseline in NTD patients, not influenced by RBC transfusion, OR
 - Reduction in RBC transfusion burden by $\geq 20\%$ over a continuous 8-week interval compared to the 8 weeks prior to the start of treatment in TD patients.
- To evaluate the time to erythroid response and duration of erythroid response.
- To evaluate the mean change from baseline over an 8- or 12-week period in hemoglobin level in NTD patients not influenced by RBC transfusion
- To evaluate the mean % change from baseline in transfusion burden over an 8- or 12-week period in TD patients.
- To evaluate the mean change in pre-transfusion hemoglobin levels in TD patients
- To evaluate changes in markers of erythropoiesis, hemolysis, iron overload, and iron metabolism
- To examine the PK profile of ACE-536 in patients with β -thalassemia

8.3. Exploratory Objectives

- To evaluate biomarkers related to the TGF- β superfamily
- To evaluate patient self-reported quality of life using tools including but not limited to the Functional Assessment of Cancer Therapy-Anemia Scale (FACT-An) and Short Form (36) Health Survey (SF-36) questionnaires
- To evaluate change in extramedullary hematopoiesis (EMH) mass size by MRI
- To evaluate change in spleen size by MRI
- To evaluate change in bone mineral density (BMD) by DXA

- To evaluate change in leg ulcers
- To evaluate change in the 6-minute walk test (6MWT) distance in NTD patients

9. OVERALL STUDY DESIGN AND PLAN: DESCRIPTION

This open-label extension study will evaluate the effects of up to 60 months of ACE-536 treatment in patients with β -thalassemia previously enrolled and treated with ACE-536 for up to 3 months in study A536-04.

9.1. Study Design

The base study (A536-04) is a phase 2, open-label, ascending dose study to evaluate the effects of ACE-536 in patients with β -thalassemia. A total of up to 64 patients may be enrolled in study A536-04 and may be eligible for study A536-06.

Consenting patients that meet the A536-06 eligibility criteria may immediately roll over from A536-04 to study A536-06 following the last ACE-536 dose. These patients may forego the End of Study (EOS) visit in study A536-04 to begin study A536-06. For these patients, Cycle 1 Day 1 (C1D1) of study A536-06 may take place 28 (\pm 7) days after the last dose administered in study A536-04, which may coincide with the patient's A536-04 End of Treatment (EOT) visit. These patients are considered "patients without treatment interruption".

Patients who complete the EOS visit for study A536-04 and are \geq 28 days post EOS visit are considered "patients with treatment interruption" and will be re-assessed for eligibility by meeting all eligibility criteria plus additional inclusion criteria, as defined in [Section 9.3](#).

Patients who do not meet the above criteria (e.g., $>$ 35 days after last dose in study A536-04 and $<$ 28 days post EOS visit in study A536-04) may still participate, but should be treated as patients with treatment interruption and should not begin study A536-06 C1D1 until they have reached \geq 28 days post EOS visit from study A536-04 so that new baseline assessments can be measured.

For patients without treatment interruption, transfusion status (NTD or TD) will carry-over from the base study A536-04. For NTD patients with treatment interruption, transfusion status will be reassessed prior to C1D1 of study A536-06. NTD patients with treatment interruption are defined as patients who require transfusion of $<$ 4 units of RBCs over the 8 weeks prior to Cycle 1 Day 1 of study A536-06. For TD patients with treatment interruption, transfusion status will carry-over from the base study A536-04.

A patient without treatment interruption may continue to be dosed with ACE-536 at the same dose level (rounded to nearest A536-06 starting dose level) administered at their last dose in study A536-04 (unless a dose reduction is required based upon patient dose modification rules from study A536-06). All patients with treatment interruption will be initially treated with ACE-536 at a starting dose level of 0.8 mg/kg which has been determined to be safe and well tolerated by the Safety Review Team (SRT) based on data from study A536-04.

Each TD patient will have a defined "pre-transfusion hemoglobin threshold" which will be calculated based on transfusion history and will be used for determining when to transfuse during the study. The baseline pre-transfusion hemoglobin threshold will be the mean of all documented pre-transfusion hemoglobin values during the 12 weeks prior to C1D1 of base study

A536-04 (for patients without treatment interruption) or study A536-06 (for patients with treatment interruption). During treatment, if the pre-transfusion hemoglobin level is increased by ≥ 1 g/dL compared to the baseline pre-transfusion hemoglobin threshold for that patient, transfusion should be delayed by a minimum of 7 days and/or the number of units transfused should be reduced by 1 or more RBC units. Patients may be transfused at the investigator's discretion for symptoms related to anemia or other requirements (e.g., infection).

Patients will participate in the extension study A536-06 for up to 97 months, including a 28-day (1 month) screening period, a 60-month treatment period and a 3-year (36 months) follow-up period.

The SRT established for study A536-04 will review safety data and PD data periodically throughout study A536-06.

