5. STATISTICAL METHODOLOGY

5.1. Definitions

Transfusion Status

For patients without treatment interruption, transfusion status (NTD or TD) will carry-over from the base study A536-04.

For NTD patients with treatment interruption, transfusion status will be reassessed prior to C1D1 of study A536-06. NTD patients with treatment interruption are defined as patients who require transfusion of < 4 units of RBCs over the 8 weeks prior to Cycle 1 Day 1 of study A536-06.

For TD patients with treatment interruption, transfusion status will carry-over from the base study A536-04.

Transfusion Dependent (TD) Defined in Base Study A536-04

Based on the protocol, TD patients are defined as those who required ≥ 4 units of RBCs every 8 weeks (confirmed over 6 months prior to study A536-04 Cycle 1 Day 1). For statistical programming purposes, a patient is defined as TD if the total RBCs is ≥ 11 units during 26 weeks on or prior to study A536-04 Cycle 1 Day 1.

Non-transfusion Dependent (NTD) Defined in Base Study A536-04

NTD patients are those who do not meet the above definition for TD. For statistical programming purposes, NTD patients are defined as those who received < 11 units of RBCs during 26 weeks on or prior to study A536-04 Cycle 1 Day 1.

Baseline

For patients who roll over to Study A536-06 without interruption, the baseline for Study A536-04 will be used as the baseline for Study A536-06 for all measurements, as further defined below. For patients who enter Study A536-06 with interruption, the baseline for Study A536-06 will be used, as further defined below. For assessments that are not scheduled to be done or with an inadequate data collection window at the beginning of Study A536-06, the baseline for Study A536-04 will be used as the baseline for Study A536-06.

Baseline Hemoglobin

Baseline hemoglobin will be the average of hemoglobin measurements within 28 days of Cycle 1 Day 1, excluding measurements within 14 days following RBC transfusion.

Baseline Transfusion Burden

Baseline transfusion burden will be calculated as the total amount of RBC transfusions during the 12 weeks on or prior to Cycle 1 day 1.

Baseline for Other Parameters

Baseline erythropoietin (EPO) is defined as the maximum test value within 28 days prior to Cycle 1 Day 1. For all other parameters, baseline is defined as the last observation on or prior to Cycle 1 Day 1.

Transfusion Unit Conversion

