5.7. Efficacy Analyses

No formal hypothesis testing is planned. All efficacy endpoint will be performed using the ITT population.

In general, the below rules apply to the derivations of efficacy endpoints which utilize hemoglobin and RBC transfusion data unless specified otherwise:

- Hemoglobin measurements within 14 days following RBC transfusion will be excluded from the efficacy analysis.
- For each patient, all efficacy endpoints will be derived based on an analysis cutoff day, defined as the last dose + 56 days or the last date from transfusion record data, whichever is earlier.

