¹⁰ **Pregnancy test** (urine or serum) and menstrual history is required prior to C1D1 for female patients of child bearing potential only.

¹¹ Transfusion history will be collected for 12 months prior to C1D1.

¹² **End of Treatment (EOT):** Should be performed 28 days (\pm 7 days) after the last dose of ACE-536. Patients who discontinue treatment early should complete the end of treatment visit at the time of discontinuation and complete the Day 141 follow up visit 28 days (\pm 7 days) after the EOT visit.

¹³ **End of Study (EOS):** Should be performed 28 days (\pm 7 days) after the Day 113/EOT visit (56 days after the last dose of ACE-536).

¹⁴ **Day 85 \pm 2 days** is the last possible study day that ACE-536 may be administered, regardless of the cycle.

¹⁵ If a **dose delay** is required per the dose modification rules the patient will not be dosed. The patient will return weekly to assess hematology results and adverse events until the patient is eligible to administer the next dose of ACE-536.

¹⁶ If the patient has a positive ADA result at their last assessment, the patient may be asked to return approximately every three months for additional testing until a negative result is obtained or the result is considered stabilized.

¹⁷ MRI for liver iron content will be performed at selected sites.

¹⁸ For the first dose of ACE-536, dosing should occur after a minimum of 7 days post-transfusion; subsequent doses should not be given within 24 hours of transfusion or planned transfusion.

¹⁹ Administration of quality of life questionnaires, including but not limited to FACT-An and SF-36 is required for patients in the expansion cohort only.

²⁰ QoL questionnaires including but not limited to FACT-An and SF-36 should be completed at the EOT visit only for expansion cohort patients who discontinue treatment early.

²¹ Abdominal ultrasound of the spleen is required for patients with no prior splenectomy in the dose escalation cohorts only. Patients in these cohorts with clinical signs of a change in spleen size or abnormality should have an abdominal ultrasound as needed throughout study.

²² Pregnancy test is not required at Day 141/EOS.

²³ Physical exam should include an optional evaluation of gonadal size in males at C1D1, EOT, and EOS visits only.

²⁴ MRI of the chest and abdomen for EMH masses and spleen, DXA for BMD and 6MWT for NTD patients will be performed in the expansion cohort patients only, at selected sites.

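### For interrupted transfusion-dependent patients, SAP 5.1 replaces the protocol's A536-04 transfusion baseline with a 12-week window that can open at or before the last A536-04 dose

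*Protocol*

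**What the plan says.** - **Re-entry.** Protocol 9.1 treats patients as interrupted once they have completed the A536-04 end-of-study (EOS) visit and are at least 28 days past it. Patients who fall between the two entry routes must also wait those 28 days, "so that new baseline assessments can be measured". The 28 days is a minimum, with no upper limit.
- **Timing of EOS.** SAP Appendix 3, note 13, places A536-04 EOS 28 (± 7) days after end of treatment (EOT), that is "56 days after the last dose of ACE-536". Note 12 places EOT 28 (± 7) days after the last dose.
- **Baseline in the SAP.** SAP 5.1 defines baseline transfusion burden as "the total amount of RBC transfusions during the 12 weeks on or prior to Cycle 1 day 1", and for interrupted patients the A536-06 baseline applies. It reverts to the A536-04 baseline where the data collection window at the start of A536-06 is inadequate, but does not define that word.
- **Baseline in the protocol.** Protocol 15.2.3 sets the pretreatment interval for transfusion-dependent (TD) patients as the 8 or 12 weeks before A536-04 Cycle 1 Day 1 (C1D1). The A536-06 pretreatment period is an additional analysis for interrupted patients.
- **Declared changes.** The table in SAP 5.12.6 covers baseline hemoglobin and the analysis populations, not this change.
- **Transfusion threshold.** Protocol 9.1 and 10.2.3 set each TD patient's threshold as the "mean of all documented" pre-transfusion hemoglobin values over 12 weeks; for interrupted patients these are the 12 weeks before A536-06 C1D1.

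**The concern.** A pretreatment baseline should describe transfusion need without the drug. The minimum wait plus the EOS interval comes to 12 weeks, which is also the length of the baseline window. An early re-starter's A536-06 baseline can therefore reach back to the last A536-04 dose.

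If that dose still reduces transfusion need during the window, baseline burden is too low and percent reduction is understated. The TD response rates at the 20%, 33% and 50% thresholds in SAP 5.7.2.1, and the mean percent change in SAP 5.7.2.3, would be biased towards no effect. The bias would vary with how soon the patient re-entered. The protocol's own reference interval avoids this, and the SAP moves away from it without saying so.

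**Working it through.** **Inputs**
- EOT is 28 ± 7 days after the last dose and EOS is 28 ± 7 days after EOT (SAP Appendix 3, notes 12 and 13). The A536-04 schedule has EOT on Day 113 and EOS on Day 141. Day 85 ± 2 "is the last possible study day that ACE-536 may be administered".
- Minimum wait after EOS: 28 days (Protocol 9.1).
- Baseline window: 12 weeks = 84 days (SAP 5.1).
- Half-life "ranged from 14.9 to 16.2 days after the first dose" and mean Tmax 7.0 to 9.8 days, in healthy postmenopausal women at up to 0.25 mg/kg (Protocol 7.3).

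**1. Reproduce the stated interval.** 141 − 85 = 56 days = 28 + 28, which agrees with the SAP.

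**2. Earliest C1D1 after the last A536-04 dose, and where the 84-day window opens**
- Nominal: 28 + 28 + 28 = 84 days. The window opens at 84 − 84 = 0, the day of the dose.
- Both visits early: 21 + 21 + 28 = 70 days. It opens 14 days before the dose.
- Both visits late: 35 + 35 + 28 = 98 days. It opens 14 days after the dose.
- Reading EOS as Day 141 ± 7 with a Day 85 dose: 134 − 85 + 28 = 77 days. It opens 7 days before the dose.

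These dates need no pharmacological assumption.

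**3. Exposure in the window (assumption: one-compartment kinetics, five doses 21 days apart).** Ignoring absorption, mean exposure over the 84 days after the last dose, as a share of the steady-state average, is

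(21/84) × (1 − r⁵)/(1 − r) × (1 − 2^(−84/h)), where r = 2^(−21/h) and h is the half-life.

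- h = 14.9: 0.25 × 1.592 × 0.980 = 0.39
- h = 16.2: 0.25 × 1.668 × 0.973 = 0.41

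With first-order absorption fitted to the stated Tmax, and the last A536-04 dosing interval as the on-treatment reference, the share is 42-46%. The span is thus 39-46%, or roughly 40-45%. With absorption it is 57-61% at a 70-day gap and 24-29% at 98 days.

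**4. What a true 50% reduction would be scored as at day 84.** If baseline burden is understated by a fraction u, the scored reduction is 1 − 0.50/(1 − u).
- *Effect proportional to exposure, with the A536-04 effect also 50%.* u = 0.50 × 0.39 = 0.195 gives 1 − 0.50/0.805 = 38%. u = 0.50 × 0.46 = 0.23 gives 1 − 0.50/0.77 = 35%. An exposure share of 0.41 gives 37%.
- *Effect only on days above half the on-treatment mean concentration (28 to 32 of the 84 in the absorption model), with burden 20-50% lower on those days.* u = (28/84) × 0.20 = 0.067 gives 1 − 0.50/0.933 = 46%. u = (32/84) × 0.50 = 0.190 gives 1 − 0.50/0.810 = 38%.

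On either assumption a patient at exactly 50% would miss the 50% threshold.

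**5. When the window clears.** No baseline day lies within 56 days of the last dose once C1D1 is at least 56 + 84 = 140 days after it. Mean modelled exposure over that window is 3-5%.

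**The case against.** The strongest reply is that the protocol already has the answer. Protocol 15.2.3 makes the A536-04 interval the reference, so the 28-day wait need not be a design fault. That stands, and it places the defect in the SAP's undeclared departure from the protocol.

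The SAP fallback may also already apply. Protocol 12.1 collects transfusion history only from A536-04 EOS to A536-06 C1D1, and SAP 4.1 limits interrupted patients to A536-06 data. At the minimum wait, that history covers 28 of the 84 days, which could well be called inadequate. This also stands as a possible reading, so it cannot be said that the fallback fails these patients. It cannot be relied on either, because the term is undefined and nothing in it mentions carry-over.

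Four stronger readings are tempting but unsupported:
- **That the drug is still acting throughout the baseline.** The half-life comes from healthy women after a first dose at lower dose levels. The documents give no duration of effect on transfusion need.
- **That two thirds of the baseline (56 of 84 days) is treated time.** SAP 5.7 ends efficacy derivation at a day "defined as the last dose + 56 days or the last date from transfusion record data, whichever is earlier". That is a data cutoff, not a statement about drug action.
- **That change in pre-transfusion hemoglobin is biased in the same way.** The 12-week mean in Protocol 9.1 is a threshold for transfusion decisions. SAP 5.7.2.3 does not say that it is also the endpoint baseline.
- **That interrupted patients in general are affected.** The 28 days is a floor, and late re-starters have a clear window.

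Finally, safety is the primary objective, efficacy is descriptive without testing, and no comparison of interrupted with rollover patients is planned. This limits the consequence. A conservative direction does not remove the problem, since the response rates are reported as estimates with exact confidence intervals.

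**Conclusion.** The point holds as a conflict between SAP and protocol with a plausible bias for early re-starters. SAP 5.1 changes the reference baseline for interrupted TD patients, SAP 5.12.6 does not declare it, and at the earliest permitted re-entry the new window opens at or before the last A536-04 dose. The dates and the conflict rest on the documents alone.

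The size rests on assumptions: kinetics carried over from healthy women, effect tied to exposure, and an A536-04 effect of 20-50% in an ascending-dose study. On those terms a true 50% reduction is scored as about 35-46% at a gap of 84 days. The understatement is larger at shorter gaps and fades by about day 140. How many patients this touches cannot be said, because the number interrupted and their gaps are not given. It merits correction before database lock but does not affect the primary safety objective.

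**What to change.** - **SAP 5.1.** State that for interrupted TD patients whose pre-C1D1 baseline window includes any day within 56 days of the last A536-04 dose, the A536-04 pretreatment interval is the baseline for transfusion burden, as in Protocol 15.2.3. Say that this counts as an inadequate window, and make SAP 4.1 agree. The 56 days borrows the SAP's own efficacy cutoff as a practical limit.
- **Reporting.** Present the A536-06-window result as a sensitivity analysis and show each interrupted patient's time since the last A536-04 dose.
- **SAP 5.12.6.** List the departure from Protocol 15.2.3.
- **SAP 5.7.2.3.** State which baseline is used for change in pre-transfusion hemoglobin.
- **Protocol 9.1 and 10.2.3.** The sponsor should reconcile the minimum wait, and its stated purpose of a new baseline, with the 12-week window for the transfusion threshold. No clinical rule is proposed here.

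The cost is one rule, one sensitivity table and a few clarifying lines. The data exist: A536-04 collects 12 months of transfusion history before its C1D1 (SAP Appendix 3, note 11). The drawbacks are an older baseline for some patients and mixed baseline sources among interrupted patients, which the sensitivity table and the listed gaps would make visible.
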